#### 5.5 Multicenter Studies

The appropriateness of pooling data across sites will be assessed using a logistic regression model including a random effect for site to test whether sites have a significant variability in the primary endpoint. If it's determined that heterogeneity by site exists, the primary endpoint results will be presented by site and the final analysis will be stratified by site. Sites with less than 10 subjects will be pooled according to study region as defined previously.

In addition, to assess the appropriateness of pooling results between study regions (North America vs. Japan vs. Europe), an assessment of the effect of region on the primary endpoint will be carried out in

	FORM	Document No BIO-TMP-0702 Revision: 00
	TITLE Statistical Analysis Plan	Effective date: 16-Mar-2018 Department: BIO

the PP and ITT populations using interaction testing between region and treatment effect from the logistic regression. A non-significant result for region will support the pooling of patients across regions for the primary safety and efficacy analysis. A significant result will require further inspection of the by-region results to assess if poolability is appropriate.

Both tests will be performed at a 15% level of significance level.

## 5.6 Safety Summaries and Analyses

### 5.6.1 Adverse Events

For site reported adverse events, number of subjects with at least one adverse event will be summarized for all subjects in the AT population overall and by event severity, relation to procedure, and relation to device. In addition, number of subjects with SAEs and UADEs will be summarized for all subjects in the AT population. Subject data listings of all adverse events and serious adverse events, with their relationship to study device/procedure, AE onset date, outcome, and duration will be presented in the data listings.

Site reported death, myocardial infarction, revascularization, stent thrombosis and bleeding events will be summarized in the ITT population as in-hospital events, at 30-days, 6 months, and 1, 2, 3, 4, and 5 years. Descriptive statistics for in-hospital events will include count, percentage, and sample size. Subjects with missing data will be excluded from the denominator. Differences in event rates between the two treatment arms will be summarized descriptively with the difference in percentages, the asymptotic 95% confidence interval for the difference of two percentages, and a p-value based on a chi-squared test. If 20% or more of the expected cell frequencies are less than 5 then a Fisher's Exact Test will be used to test for differences in proportions.

Survival analysis techniques, as detailed in Section 4.3, will be used to analyze the site reported events at 30 days, 6 months, and 1, 2, 3, 4, and 5 years. Summary statistics will include Kaplan-Meier estimated event rates and number of events. The log-rank test will be used for comparing treatments. Hazard ratios and the associated two-sided confidence intervals (Wald's CI) will be estimated by Cox proportional hazards model, including treatment as a covariate.

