### 8.7.2 Relatedness

The investigator will use the following definitions to assess the relationship to the study device or procedure:

Not related	The cause of the AE is known and the event is not related to the study device or procedure.
Unlikely to be related	There is little or no temporal relationship to the study device or procedure, and/or a more likely alternative etiology exists.
Possibly related	There is a reasonable possibility that the event may have been caused by the study device or procedure. The AE has a timely relationship to the study device or procedure(s); however, follows no known pattern of response , and an alternative cause seems more likely or there is significant uncertainty about the cause of the event.

Related	A related event has a strong temporal relationship and an alternative cause is unlikely.
----------------	--------------------------------------------------------------------------------------------------------

If the relationship between any adverse event and the use of the investigational medical device is considered to be possibly related or related, that event will be classified as an ADE or SADE.

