### **10.2 Clinical Events Committee (CEC)**

An independent Clinical Events Committee (CEC) will adjudicate all site-reported adverse events that represent a potential endpoint event in an ongoing fashion during the trial. Relationship of these events to the study device and procedure will also be adjudicated.

The CEC will include cardiologists and/or interventional cardiologists experienced in clinical trials who are otherwise independent of the Sponsor and the conduct of the study. Members will not have scientific, financial or other conflicts of interest related to SINOMED or the Investigators. The CEC will operate and

conduct all meetings and event reviews independent of the Sponsor unless specific expert knowledge regarding the characteristics or function of the study device is requested by the CEC from the Sponsor.

The CEC will meet regularly throughout the study to adjudicate events in an ongoing and timely fashion. The adjudication process, event definitions and required source document materials for each type of event will be pre-specified in the CEC Charter prior to the onset of the trial. The adjudication process will include CEC member review of data collected from all relevant medical records, as well as all imaging studies, associated with an event. All adjudication decisions will be made by the CEC in an independent fashion based upon review of all available medical evidence.

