### 11.4.7 Additional Analyses

The following data will be summarized using descriptive statistics presented by treatment group in the ITT and PP populations:

- Subject enrollment and data compliance by site and visit (data compliance at each visit is the percentage of patients whose data forms have been collected and entered divided by the percentage of patients whose forms should have been collected and entered)
- Frequency (number and percentage of patients) with each type of concomitant medication
- Frequency (number and percentage of patients) with each site-reported Treatment Emergent AE overall and by MedDRA system organ class and preferred term (a treatment emergent AE is an AE that started or worsened during or after the index procedure)
- Frequency (number and percent of patients) with each site-reported Treatment Emergent Serious AE overall and by MedDRA system organ class and preferred term
- Frequency (number and percent of patients) with each site-reported Treatment Emergent AE or SAE, by CEC-adjudicated relationship to the investigational device or procedure
- Protocol deviations (number and percentage of patients with each deviation type)
- Detailed listings on primary and secondary endpoints, site-reported AE, and protocol deviations

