### 11.5.3 Independent Assessments

To decrease the variability of clinical outcome measurements, all adverse events, including all potential endpoint events, will be adjudicated by an independent CEC according to standardized endpoint definitions, and the relationship of these events to the study device will also be adjudicated. In addition, an independent Angiographic Core Laboratory analysis will be performed by technicians who are blinded to subject treatment assignment to provide accurate and unbiased determinations of lesion and device success, as well as to determine if revascularizations meet the diameter stenosis criteria for classification as clinically-driven.

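### The SAP omits the protocol's by-arm summary of adverse events by CEC-adjudicated relationship and keeps only a relatedness summary whose assessor it does not name

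*SAP*

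**What the plan says.** **Protocol.** Section 11.4.7 lists outputs to be given as "descriptive statistics presented by treatment group in the ITT and PP populations". One of them is the frequency of patients "with each site-reported Treatment Emergent AE or SAE, by CEC-adjudicated relationship to the investigational device or procedure". The CEC has the matching task. Section 10.2 says "Relationship of these events to the study device and procedure will also be adjudicated", and 11.5.3 says that "the relationship of these events to the study device will also be adjudicated". CEC members are blinded (11.5.2). For the site record, 8.7.2 states "The investigator will use the following definitions to assess the relationship to the study device or procedure". A rating of possibly related or related makes the event an ADE or SADE.

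**SAP.** Section 5.6.1 starts from site-reported events. Subjects with at least one AE are to be "summarized for all subjects in the AT population overall and by event severity, relation to procedure, and relation to device", and subjects with SAEs and UADEs are counted. The section refers to the CEC nowhere. In SAP 7.1 the only AE characteristics table is Table 30, in the AT population, and the AE and SAE listings (13 and 14) carry no CEC label.

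**The concern.** Whether an event is device-related is a judgement, and the protocol's possibly related category is meant for cases with real uncertainty about cause. A rater who knows which stent was implanted may rate an investigational stent differently from a marketed one, in either direction. The protocol answers this by having a blinded committee rate the relationship and by tabulating that rating by arm. If the study outputs follow the SAP alone, the table actually produced may hold the unblinded rating, and the blinded rating may never be shown.

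The relatedness rows also carry weight. SAP 5.6.1 plans no separate ADE or SADE summary, so these rows are where a reader would look for device-related events in each arm.

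**Working it through.** No figure in the plan bears on this point, so the check is a comparison of texts.

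| Item | Protocol 11.4.7 | SAP 5.6.1 and 7.1 |
|---|---|---|
| Events | Site-reported treatment-emergent AEs and SAEs | Site-reported AEs |
| Whose relatedness rating | CEC | Not stated |
| Population | ITT and PP | AT |
| By arm | Yes | Yes, through the general rule in SAP 4.3 |
| Output listed | Yes | Table 30 only; no table or listing of CEC relationship |

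1. *Is the CEC relationship analysed anywhere in the SAP?* No. The SAP uses CEC adjudication for endpoint events (sections 2.1 to 2.2.3; Tables 13 and 18 to 25; Listings 8 to 12). No section, table or listing reports a CEC rating of relationship to device or procedure.

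2. *Whose rating would fill Table 30?* The words site reported in 5.6.1 do not settle it, because the protocol's CEC-relationship summary also starts from site-reported events. Two things point to the investigator's rating. It is the only site-level rating the protocol defines (8.7, 8.7.2). And the SAP usually labels its source: CEC adjudicated for the outputs named in step 1, site reported for Tables 26 to 29. Table 30 has neither label. This is an indication and not proof, since Tables 14 to 16 also lack a source label although they concern adjudicated endpoints.

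3. *Is that rater blinded?* Protocol 11.5.2 describes a single-blind study. It lists as blinded the subject and family, site personnel doing follow-up evaluations, the CEC and the core laboratory technicians. The implanting investigator is not listed. The same section foresees a site investigator disclosing the allocation to a subject, which presupposes knowing it. Follow-up personnel have no access to the randomization forms, and records are meant to use a neutral device term. Exposure is therefore greatest around the procedure and smaller afterwards. It may not vanish later, because 8.8.1 makes the investigator responsible for AE assessment throughout.

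4. *Does the change of population matter?* AT classifies subjects by treatment received and adds non-randomized subjects given a study stent (SAP 3.4). It is a reasonable safety set, but it is not the randomized comparison that 11.4.7 specifies.

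5. *For which events will a CEC rating exist?* The protocol disagrees with itself. Section 10.2 says the CEC "will adjudicate all site-reported adverse events that represent a potential endpoint event", and the synopsis agrees. Section 11.5.3 extends adjudication to all adverse events. It and the synopsis mention relationship to the device only, while 10.2 covers device and procedure.

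6. *Is the omission explained?* No. SAP 1.0 and 8.0 say the SAP is based on protocol version 8.0, which contains 11.4.7. The SAP's change table records nothing for version 1.

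**The case against.** The strongest reply is that nothing has been withdrawn. SAP 1.0 says the SAP supplements the protocol and that significant modifications will appear in an amendment or the study report, so 11.4.7 formally still applies. Section 5.6.1 names no assessor, and Table 30 is only a title that could hold either rating. This stands. A reader might infer that the SAP has replaced the CEC rating with the investigator's or cancelled the analysis; the documents show only silence. But the same section presents the SAP as the detailed methodology, and an analysis with neither text nor a table in it is easily missed.

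A second reply is that the main measures of device harm are untouched. TLF, clinically driven revascularization, MACE, death, MI, stent thrombosis and bleeding are all adjudicated by the CEC and reported by arm. This also stands. It rules out the tempting inference that the comparison of device-related harm as a whole rests on unblinded raters. No hypothesis or success criterion uses the relatedness rating.

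A third reply is that, if 10.2 governs, the CEC table covers mostly events already reported by arm as endpoints, and other AEs have only the site rating. That is a reason to keep the site-rated table and state the denominator. It is not a reason to leave out the CEC table, because the endpoint tables do not say whether an event was attributed to the device or the procedure.

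**Conclusion.** The point holds as an unexplained gap between protocol and SAP. A summary the protocol specifies, using a blinded rating and the ITT and PP populations, has no place in the SAP. The relatedness summary that remains does not name its assessor and would most naturally be filled with the investigator's rating in AT.

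The consequence is limited to blinded attribution of events to device or procedure. The possible bias is concentrated in periprocedural events and could run either way. Its size cannot be estimated: the documents give no rate of arguable events and no rate of disagreement between site and CEC, so any ratio between arms would be an assumption. The primary and powered secondary conclusions are unaffected.

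This rests on two readings: that Table 30 would use the site rating unless told otherwise, and that the CEC will record relationship for at least the potential endpoint events, as 10.2 states.

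**What to change.** - Add the 11.4.7 summary to SAP 5.6.1 and as a numbered table in SAP 7.1: treatment-emergent AEs and SAEs by CEC-adjudicated relationship to device and to procedure, by randomized arm, in ITT and PP.
- Name the assessor (investigator or CEC) in the title of every relatedness table and listing. Keep the site-rated AT table alongside.
- Reconcile the CEC's scope between the synopsis and Protocol 10.2 on one side and 11.5.3 on the other, including whether relationship to the procedure is rated. State the resulting denominator in the table.
- Optional: cross-tabulate site against CEC rating by arm. The protocol does not ask for this, but it would show whether the two raters differ by arm.

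The cost is SAP wording and one or two descriptive tables from adjudication data the protocol already plans to collect. No hypothesis, alpha or sample size changes. The drawback is that the CEC table may cover only the events the CEC reviews, so it cannot replace the broader site-rated table.

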### 5.6.2 Device Deficiencies, Malfunctions

All device deficiencies, malfunctions, use errors, and any (serious) adverse events associated with device malfunctions/deficiencies/use errors, as documented in the case report form, will be summarized descriptively by frequency (number and percentage of subjects) in the ITT Population for all subjects and by treatment arm.

	FORM	Document No BIO-TMP-0702 Revision: 00
	TITLE Statistical Analysis Plan	Effective date: 16-Mar-2018 Department: BIO

### 5.6.3 **Laboratory Data**

Analysis of the clinical laboratory data will be performed on the ITT analysis population and summarized descriptively for each visit for all subjects and by treatment arm.

Cardiac biomarkers Troponin (I or T) or CK-MB will be collected at baseline/pre-procedure and post-procedure/discharge. If serial biomarker measurements are taken at a time point, the peak (i.e., the highest) biomarker value will be included in the analysis for that time point.

For cardiac biomarkers, the frequency and percentage of subjects falling into each of the following categories will be presented separately for pre-procedure/baseline and post-procedure/pre-discharge visits:

For CK-MB:

≤ULN, >1 X ULN, ≥ 1-3ULN, ≥ 3 x ULN, ≥ 3-5ULN, ≥ 5 x ULN, ≥5-10ULN, ≥ 10 x ULN

For Troponin (I or T):

≤ULN, >1 X ULN, ≥ 1-3ULN, ≥ 3 x ULN, ≥ 3-5ULN, ≥ 5 x ULN, ≥5-10ULN, ≥ 10 x ULN, ≥ 10-35 ULN, ≥ 35 ULN, ≥35-70XULN, ≥70ULN

### 5.6.4 **Electrocardiogram**

Abnormal ECG findings and/or significant ECG changes compared to prior time points will be summarized descriptively by frequency (number and percentage of subjects) in the ITT Population for all subjects and by treatment arm.

### 5.6.5 **Anginal Status**

Anginal status (CCS classification, Braunwald classification of unstable angina, or silent ischemia) will be collected at screening/baseline, post-procedure or pre-discharge, and at 30 days, 6 months, and 1, 2, 3, 4, and 5 years and summarized descriptively by frequency (number and percentage of subjects) in the ITT Population for all subjects and by treatment arm.

### 5.6.6 **Concomitant Medications**

Concomitant medication use, including compliance to DAPT, will be summarized by frequency (number and percentage of subjects) at each visit for all subjects and by treatment arm based on the ITT analysis population. In addition to concomitant medication use, antiplatelet and anti-coagulant medications administered during baseline procedure will be presented for the procedure visit.

	FORM	Document № BIO-TMP-0702 Revision: 00
	TITLE Statistical Analysis Plan	Effective date: 16-Mar-2018 Department: BIO

## 7.0 APPENDICES

### 7.1 List of Tables, Listings, and Figures

Tables:

- 1) Patient Enrollment and Disposition
- 2) Enrollment by Country (ITT)
- 3) Summary of Visit Compliance, Overall and by Site (ITT)
- 4) Summary of Protocol Deviations (ITT)
- 5) Summary of Major Protocol Deviations (ITT)
- 6) Inclusion or Exclusion Criteria Deviations (ITT)
- 7) Summary of Demographics and Baseline Vital Signs (ITT, PP)
- 8) Baseline Risk Factors and Medical history (ITT, PP)
- 9) Summary of Site Reported Procedure Characteristics (ITT, PP)
- 10) Summary of Procedural Medications (ITT, PP)
- 11) Summary of Site Reported Lesion Characteristics (ITT, PP)
- 12) Summary of Device Utilization by Device Size (AT)
- 13) Primary Endpoint Analysis of TLF at 12 Months – CEC Adjudicated (ITT, PP, MPP)
- 14) Sensitivity Analysis of Primary Endpoint at 12 Months (ITT, PP)
- 15) Subgroup Analysis of the Primary Endpoint of TLF at 12 Months (ITT, PP)
- 16) Summary of MI Event Types According to Multiples of the 99th Percentile Upper Reference Limit of Cardiac Biomarkers (ITT)
- 17) Summary of Acute Success Defined by QCA (ITT, PP)
- 18) Summary of CEC Adjudicated In-Hospital Clinical Events (ITT, PP)
- 19) Summary of In-Hospital CEC Adjudicated Revascularization, Bleeding, and Stent Thrombosis Events (ITT, PP)
- 20) Summary of CEC Adjudicated Clinical Events within 30 Days of Randomization (ITT, PP)
- 21) Summary of CEC Adjudicated Revascularization, Bleeding, and Stent Thrombosis Events within 30 Days of Randomization (ITT, PP)
- 22) Summary of CEC Adjudicated Clinical Events within 6 Months of Randomization (ITT, PP)
- 23) Summary of CEC Adjudicated Revascularization, Bleeding, and Stent Thrombosis Events within 6 Months of Randomization (ITT, PP)
- 24) Summary of CEC Adjudicated Clinical Events within 1 Year (2, 3, 4, 5 Years) of Randomization (ITT, PP)
- 25) Summary of CEC Adjudicated Revascularization, Bleeding, and Stent Thrombosis Events within 1 Year (2, 3, 4, 5 Years) of Randomization (ITT, PP)
- 26) Summary of Site Reported In-Hospital Clinical Events (ITT)
- 27) Summary of Site Reported 30 Day Clinical Events (ITT)
- 28) Summary of Site Reported 6 Month Clinical Events (ITT)
- 29) Summary of Site Reported 1 Year (2, 3, 4, 5 Year) Clinical Events (ITT)
- 30) Summary of Adverse Event Characteristics (AT)
- 31) Summary of Device Deficiencies, Malfunctions, Use Errors or Device Misuse (ITT)

	FORM	Document No BIO-TMP-0702 Revision: 00
	TITLE Statistical Analysis Plan	Effective date: 16-Mar-2018 Department: BIO

- 32) Summary of Concomitant Medications (ITT)
- 33) Summary of Angina Status by Visit and Treatment (ITT)
- 34) Summary of ECG Data by Visit and Treatment (ITT)
- 35) Summary of Pre- and Post-Procedure QCA Measurements from Angiographic Core Lab (ITT)
- 36) Summary of Pre-Procedure Lesion Morphology from ACL (ITT)
- 37) Summary of Post-Procedure Morphology from ACL (ITT)
- 38) Summary of Stent Edge Measurements from ACL (ITT)
- 39) Summary of Stent Overlap and Gap Analysis from ACL (ITT)
- 40) Summary of Vessel Level Characteristics Assessed by the ACL (ITT)

**Listings:**

- 1) Listing of Discontinued Subjects within 1 Year
- 2) Listing of Subjects with Protocol Deviations
- 3) Listing of Subjects Excluded from Analysis Populations
- 4) Listing of Demographics and Baseline Information
- 5) Listing of Visit Compliance
- 6) Listing of Primary Endpoint Data
- 7) Listing of Device, Lesion, and Procedure Success Data
- 8) Listing of Death Events within 1 Year – CEC Adjudicated
- 9) Listing of Myocardial Infarction Events within 1 Year – CEC Adjudicated
- 10) Listing of Revascularizations within 1 Year – CEC Adjudicated
- 11) Listing of Stent Thrombosis Events within 1 Year – CEC Adjudicated
- 12) Listing of Bleeding Events (BARC Definition) within 1 year – CEC Adjudicated
- 13) Listing of Adverse Events at 1 Year
- 14) Listing of Serious Adverse Events
- 15) Listing of Unanticipated Adverse Device Effects
- 16) Listing of Device Deficiencies/Malfunctions
- 17) Listing of Subjects affected by the COVID-19 related Study Disruptions

**Figures**

- 1) Patient Disposition Flowcharts (ITT, PP, MPP, and AT populations)
- 2) KM Figures for TLF, TVF, MACE and ST at 1, 2, 3, 4, and 5 Years
- 3) Tipping Point Analysis for TLF at 1 Year

	FORM	Document № BIO-TMP-0702 Revision: 00
	TITLE Statistical Analysis Plan	Effective date: 16-Mar-2018 Department: BIO

## 8.0 VERSION HISTORY

This Statistical Analysis Plan (SAP) for study SIN-US-001 is based on the protocol version 8.0.

**Table 3 Summary of Major Changes in SAP Amendments**

SAP Version	Change	Rationale
1	Not Applicable	Not Applicable
